**Methodology:**

This is a Phase 3, randomized, open-label, multicenter study comparing the efficacy, safety and tolerability of rovalpituzumab tesirine (Arm A) versus topotecan (Arm B) in subjects with advanced or metastatic DLL3high SCLC who have first disease progression during or following front-line platinum-based chemotherapy. Subjects will be randomized in a 2:1 ratio to receive 0.3 mg/kg rovalpituzumab tesirine or 1.5 mg/m^2 (or per the local label) topotecan. Subjects receiving rovalpituzumab tesirine will also receive 8 mg orally (PO) of dexamethasone twice daily on Day -1, Day 1, and Day 2 of each cycle in which rovalpituzumab tesirine is administered.

Randomization will be stratified by prior history of brain metastases (yes versus no), prior PCI (yes vs. no) for subjects with no prior history of brain metastases, sensitivity to first line platinum-based regimen [sensitive (OR/SD after first line therapy and progression/recurrence-free interval  $\geq$  90 days) versus refractory/resistant (PD as best response to or  $<$  90 days progression/recurrence-free interval after first line therapy)] and LDH ( $>$  ULN vs.  $\leq$  ULN) at screening.

Survival Follow-up will continue until the endpoint of death, the subject becomes lost to follow-up or withdraws consent, termination of the study by AbbVie, or until 12 February 2020 whichever occurs first.

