##### **5.3.1.1 Study Procedures**

Unless otherwise stated, the baseline measurement for any given variable will be defined as the last value obtained for the variable prior to the first dose of investigational product.

The collection of tumor material for DLL3 testing may be done at any time after the informed consent is signed and prior to randomization. Screening procedures and radiographic assessments (CT scan or MRI) must be performed within 28 days prior to randomization. Randomization of the subject in the Interactive Response Technology (IRT) may occur within 3 calendar days prior to C1D1.

Subsequent study procedures should be performed within 3 business days prior to the scheduled treatment visit. For visits where no treatment is administered, procedures may be performed within  $\pm 3$  day window relative to due date. Radiographic assessments must be scheduled so that the results are known prior to the treatment visit. Post-treatment follow up, and survival follow up phase visits may occur within  $\pm 1$  week window relative to due date unless otherwise indicated.

The results of all screening and evaluations at the time of randomization must be within clinically acceptable limits, upon review by the investigator, before a subject can be randomized. Subjects will not be randomized in the study if laboratory or other screening results are unacceptable. Subjects are allowed to rescreen and have laboratory samples redrawn to meet eligibility within the same 28 day screening window. Subjects who meet the inclusion criteria and do not meet any of the exclusion criteria may be randomized. Therapeutic Area Medical Director (TAMD) review and approval is required in cases where a second rescreen is required.

Subjects receiving additional doses of rovalpituzumab tesirine as described in Section 5.3.1.1 and Section 5.5.2 will follow the same study schedule from Day 1 through EOT and PTFU as in Cycles 1 and 2.

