## **8.2 Safety Analyses**

Safety endpoints will be summarized using data from the Safety set. Safety analyses will involve examination of the incidence, severity, and type of treatment-emergent adverse events (TEAEs) reported, changes in vital signs and laboratory test results from baseline (the assessment prior to first dose) to specified time points throughout the study, and concomitant medications used. NCI CTCAE version 4.0 will be used in the grading of adverse events and laboratory abnormalities that are reported as adverse events.

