7.0 Analysis Conventions

This section provides general considerations for data handling, summary, and analysis. This also includes general definitions of certain kinds of endpoints.

Continuous variables will be summarized by sample size (N), mean, standard deviation (St. Dev.), median, minimum, and maximum. Frequency and percentage will be provided for categorical variables and 95% confidence intervals (CIs) will be generated for parameter estimates of interest, unless specified otherwise.

For the analysis of efficacy endpoints, the Randomized Set will be the primary analysis set whereas the Per Protocol Set (PPS) will be used for supportive analysis only. Analysis for the sub-groups will be carried out in the subset of Randomized Set meeting the sub-group selection criteria at the enrollment.

The change from baseline analysis for the QOL measures, patients with missing baseline values will be excluded. Descriptive summaries for the efficacy endpoints will be reported by treatment groups. These summaries will also be reported at the individual levels of each stratification factors.

The statistical comparisons for the primary and secondary endpoints will be made according to the multiplicity adjustment plan described in Section 5.7.2 to preserve the familywise one-sided type 1 error rate at 0.025. The statistical comparisons for all the other exploratory efficacy endpoints will be performed at a nominal one-sided 2.5% significance level. Confidence intervals for parameters (e.g., median survival times, HR) will be constructed with 2-sided 95% confidence level, whenever applicable. No type I error adjustment for multiple comparisons will be carried out for these exploratory endpoints.

Dealing with Multiple Values on the Same Day

In case multiple values are collected on the same day at a baseline or post-baseline visit, the arithmetic average (for continuous summary) will be used for analyses unless otherwise specified.

Definition of Baseline Observation

Unless otherwise specified, the baseline observation is defined as the last non-missing measurement collected prior to the first dose date of any study drug (rovalpituzumab tesirine or dexamethasone) for Arm A; topotecan for Arm B).

Definition of Final Observation for Laboratory and Vital Sign Parameters

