For lab and vital sign parameters, the final observation is defined as the last non-missing post-baseline measurement collected not more than 70 days after the last dose of investigational product.

Missing Data

No missing data imputation will be implemented, unless specified otherwise.

Definition of Study Day (Day Relative to the day of Randomization) and Rx Day (Day Relative to the First Dose of Study Drug)

Study Day of any observation is defined for post-randomization observations as:

$$\text{Study Day} = \text{Date of observation} - \text{Date of randomization} + 1,$$

and for observations pre-dating randomization as:

$$\text{Study Day} = \text{Date of observation} - \text{Date of randomization}.$$

Thus, the day of randomization is defined as Study Day 1, while the day prior to the randomization is defined as Study Day -1 (there is no Study Day 0).

Study Rx Day of any post-baseline observation is defined as the number of days from the day of the first dose of any study drug (rovalpituzumab tesirine or topotecan) to the date of observation. It is calculated for each observation as follows:

- Study Rx Day = Date of observation – Date of first dose of any study drug + 1

Definition of Analysis Windows

All time points and corresponding time windows are based on Study Rx Days, unless specified otherwise. For analysis at visit, especially for the laboratory data (hematology, chemistry, and urinalysis), nominal days and visit windows for the 2 treatment arms (Arm A and Arm B) are given in the table below. If more than one observation is included in a time window, the observation closest to the nominal day should be used. If there are two observations equally distant to the nominal day, the later one will be used in analyses.

Table 1. Visit Window laboratory and vital sign analysis

Study Visit (Week)	Nominal Study Rx Day	Time Window (Study Rx Days Range)
Baseline		Baseline definition
3	22	2 to \leq 32
6	43	33 to \leq 53
...
$3 \cdot X$	$7 \cdot 3 \cdot X + 1$	$7 \cdot 3 \cdot X - 9$ to $\leq 7 \cdot 3 \cdot X + 11$

The endpoints based on subject self-reported health related quality of life (QoL) and symptom assessments will be analyzed for post-treatment Week 3, Week 7 and subsequently with the increment of 6 weeks (i.e., Week 13, Week 19, and Week 24). The visit windows for the PRO endpoints are defined in [Table 2](#) below.

Table 2. Visit Window for PRO analysis

Study Visit (Week)	Nominal Study Rx Day	Time Window (Study Rx Days Range)

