12.4 Analysis of Laboratory, Vital Signs, and ECG Data

Clinical laboratory variables are listed in [Table 4](#).

For laboratory (hematology, chemistry, urinalysis, and coagulation), vital signs, and ECG parameters, changes from baseline are analyzed for each post-baseline visit (as specified in Section 7.0 Analysis of Conventions) and the final visit. If more than one measurement exists for a subject on a particular day, an arithmetic average will be calculated. The average will be considered to be the subject's measurement of that day.

Descriptive statistics will be presented for baseline, each post-baseline, and the final visit by each treatment arm. Mean change from baseline to each post-baseline visit and the final visit within each treatment arm will also be presented. The highest and lowest values of each parameter will be identified for each subject, and descriptive statistics for mean change from baseline within each treatment arm will be presented.

Laboratory grade determinations will be categorized according to NCI CTCAE version 4.0 grades, and shifts from baseline grades to maximum and final post-baseline grades will be assessed. The baseline and final grades will be defined respectively as the grade of the last measurement collected prior to or on the first dose of study drug, and as the grade of the last post-baseline measurement collected no more than 70 days after the last dose of study drug. Frequency and percentage of subjects will be presented by treatment arm: 1) baseline grade vs. maximum post-baseline grades, and 2) baseline grade vs. final post-baseline grade. Frequency and percentage of subjects experiencing a shift from baseline grades of 0 to 2 to maximum post-baseline grades of 3 to 4, and from baseline grades of 0 to 2 to final post-baseline grades of 3 to 4 will be presented by treatment arm.

Detailed listings of data for subjects experiencing NCI CTCAE grade 3 to 4 biochemistry and hematology values will be provided. All measurements collected, regardless of the number of days after the last dose of study drug, will be included in these listings. A

listing will be provided for out-of-normal range as well as clinically significant abnormal lab values.

Descriptive summary statistics for categorical ECG data will be presented for baseline and post-baseline visits; change from baseline in ECG measurements (eg QTcF) will also be summarized. Shift tables will also be provided.

Table 4. Clinical Laboratory Tests

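### SAP 7.0's date-based baseline rule leaves pre-infusion Cycle 1 Day 1 vital signs, and any laboratory tests repeated that day, outside both baseline and the by-visit windows

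*SAP*

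**What the plan says.** Four places define baseline, in three different ways.

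- **SAP 7.0, general rule.** Baseline is "the last non-missing measurement collected prior to the first dose date of any study drug". For Arm A, study drug here means rovalpituzumab tesirine or dexamethasone; for Arm B it means topotecan. The test is on the calendar date, and the date must precede the first dose date. The sentence opens with an escape clause: "Unless otherwise specified, the baseline observation is defined as".
- **SAP 12.4, laboratory grades.** The baseline grade is "the grade of the last measurement collected prior to or on the first dose of study drug". This includes the dosing date.
- **Protocol 5.3.1.1.** Baseline is "the last value obtained for the variable prior to the first dose of investigational product", so a pre-dose value on the dosing day qualifies. Protocol 8.2 agrees: it measures change "from baseline (the assessment prior to first dose").

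Two further rules decide what happens to values that are not baseline. SAP 7.0 counts Rx Days from "the day of the first dose of any study drug (rovalpituzumab tesirine or topotecan"), with no mention of dexamethasone. SAP Table 1 (laboratory and vital signs) and Table 2 (patient-reported outcomes) both open their first post-baseline window at Rx Day 2.

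In Arm A the protocol gives "dexamethasone twice daily on Day -1, Day 1, and Day 2 of each cycle" in which rovalpituzumab tesirine is given.

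**The concern.** A value measured just before the first infusion is normally the best baseline available. The SAP's general rule excludes it because it carries the dosing date, and the visit windows do not pick it up either. The by-visit tables would then start from an older screening value, in a population with progressing second-line disease whose condition can change within weeks.

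Weight and blood pressure matter most here. They are repeated on Cycle 1 Day 1 by design, they bear on the fluid-retention signal, and three of the four vital-sign criteria in SAP 12.6 (systolic pressure, diastolic pressure and pulse) depend partly on change from baseline. For some laboratory tests, the mean-change and grade-shift tables in one section could start from different values for the same subject.

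**Working it through.** No sample-size or alpha figure is involved. The check classifies each observation date under each rule.

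**Inputs**

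- Rx Day = observation date - first rovalpituzumab tesirine or topotecan date + 1 (SAP 7.0). The SAP defines this for post-baseline values only; it is extended backwards here to place earlier dates.
- First windows: Rx Day 2 to 32 (Table 1) and 2 to 28 (Table 2).
- Dexamethasone starts on Day -1 in Arm A.
- Screening is within 28 days before randomization, and randomization within 3 calendar days before Cycle 1 Day 1 (Protocol 5.3.1.1).

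**Window check.** The Table 1 formula at X = 2 gives 42 - 9 = 33 to 42 + 11 = 53, nominal day 43, as printed. At X = 1 it gives 12 to 32; the table extends the lower bound to 2, so no window reaches Rx Day 1. The Table 2 formula at X = 0 gives 49 - 20 = 29 to 49 + 21 = 70, as printed.

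**Eligibility as baseline, by date of the value**

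| Value dated | Rx Day | SAP 7.0 | SAP 12.4 (laboratory grade) | Protocol | By-visit window |
|---|---|---|---|---|---|
| Arm A, Day -2 | -1 | yes | yes | yes | none |
| Arm A, Day -1 | 0 | no | yes | yes | none |
| Arm A, Cycle 1 Day 1 pre-infusion | 1 | no | yes, or no if dexamethasone counts | yes | none |
| Arm B, Day -1 | 0 | yes | yes | yes | none |
| Arm B, Cycle 1 Day 1 pre-infusion | 1 | no | yes | yes | none |
| Either arm, Day 2 | 2 | no | no | no | Week 3 |

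Arm A loses two calendar days and Arm B one. Later cycles are safe: Cycle 2 Day 1 is Rx Day 42 + 1 = 43 in Arm A and 21 + 1 = 22 in Arm B, both inside Table 1 windows.

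**Which measurements are affected**

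- *Vital signs and weight.* Protocol Appendix C notes e and i, and Appendix D notes d and h, exempt vital signs from the no-repeat allowance and require them before the infusion, Cycle 1 Day 1 included. Essentially all treated subjects have such a value.
- *Laboratory tests.* Under Protocol 5.3.1.1, Appendix C note k and Appendix D note j, they need not be repeated if screening was within 7 days of Cycle 1 Day 1. A subject without a repeat has no Day 1 value, and normally the same screening baseline under all three rules. If the repeat was made because screening was older than 7 days, the fallback is more than 7 and at most 28 + 3 = 31 days old. If it was clinically indicated, the fallback may be more recent.
- *ECOG.* Note e lets screening procedures other than vital signs go unrepeated if done within 28 days of randomization, so there may be no Day 1 value to lose.

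**Same test, two tables.** For a laboratory test with a Cycle 1 Day 1 value in Arm B, mean change (SAP 7.0) starts from screening and the grade shift (SAP 12.4) from Day 1. In Arm A the same happens if study drug in 12.4 means rovalpituzumab tesirine, and for a Day -1 value under either meaning. Read literally, 12.4 also admits a Day 1 value taken after the infusion.

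**Unwindowed summaries.** Highest and lowest values, maximum grade and final observation use no windows, and the SAP does not define post-baseline. A pre-infusion Day 1 value that is not baseline could be counted there as on-treatment.

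**The case against.** Four points can fairly be made for the plan.

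1. *The escape clause.* SAP 7.0 allows other sections to specify otherwise, and 12.4 does. The departure is formally permitted, but it covers laboratory grades only. Mean changes, vital signs and weight stay under the general rule, and the permission does not make two baselines for one test coherent.
2. *The dexamethasone cut-off.* One principle, that baseline precedes any study treatment, gives Arm A the earlier date because its regimen starts earlier. Taken alone, that is a defensible choice. What does not stand is using study drug in two senses within SAP 7.0: the baseline rule includes dexamethasone and the Rx Day rule does not.
3. *The remedy's cost.* Counting Day 1 values makes Arm A baselines post-steroid while Arm B's stay untreated. With two doses on Day -1 and one at least 30 minutes before infusion, an Arm A Day 1 value may follow 2 + 1 = 3 dexamethasone doses. This stands, and the remedy has to deal with it.
4. *Small consequence.* The safety tables are descriptive. Protocol 8.0 now rules out statistical testing of the efficacy endpoints, and the amended schedules stop patient-reported outcome collection after Cycle 1 Day 1. This limits the stakes but does not remove the contradiction with the protocol.

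A reader might also infer that every pre-dose Day 1 measurement is lost, or that the lost values appear nowhere. The documents do not support either. Only values dated Cycle 1 Day 1 (plus Day -1 in Arm A) are affected. An assessment under the schedule's -3 day allowance keeps its eligibility if dated before Cycle 1 Day 1 in Arm B, or before Day -1 in Arm A. Exclusion from post-baseline is shown only for windowed tables.

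**Conclusion.** The point holds within limits, and the SAP should be changed. Followed literally, SAP 7.0 drops a same-day pre-infusion value from the baseline and by-visit tables, contrary to Protocol 5.3.1.1 and 8.2. This applies to vital signs and weight in essentially all treated subjects, and to laboratory tests only in those with a Cycle 1 Day 1 repeat (or an Arm A Day -1 value). The 31-day age is a ceiling from the scheduling rules, not a typical value. The documents give no distribution of screening dates, so the size of any shift in the tables cannot be estimated.

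It would be tempting to say that shift tables in general conflict with change-from-baseline tables. Only the laboratory-grade shifts have their own baseline rule; ECG and ECOG shifts follow SAP 7.0.

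The outputs affected are the descriptive change-from-baseline, laboratory-shift and vital-sign-criteria tables in SAP 12.4 and 12.6. Overall survival is unaffected. The conclusion assumes that the first dose date is programmed as a calendar date, as the wording says.

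**What to change.** In SAP 7.0 and 12.4, for both arms:

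- Define baseline once, following the protocol: the last non-missing value before the first infusion of rovalpituzumab tesirine or topotecan. Count Cycle 1 Day 1 values collected before the infusion and exclude Day 1 values collected after it.
- Define post-baseline as after that infusion, so that highest/lowest, maximum-grade and final-observation summaries cannot take in a pre-treatment value.
- State that dexamethasone does not set the cut-off, so that baseline and Rx Day share one anchor.
- For steroid-sensitive laboratory tests (glucose, leukocytes), add a supplementary summary of change from the last pre-dexamethasone value in Arm A.

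The cost is a few lines of SAP text, one derivation rule, and a convention for Day 1 values with no recorded time. The SAP describes itself as a draft to be finalized before any comparative analysis by arm, so the change can be made in time. The downside is that Arm A Day 1 baselines may follow up to three dexamethasone doses. The supplementary summary makes this visible but does not remove it from the main tables.

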7.1 Data Handling Convention at Database Level

There is no applicable data handling convention at database level.

8.0 Demographics, Baseline Characteristics, Medical History, Previous/Concomitant Medications, and Prior Oncology Therapies

Data for demographic, baseline characteristics, medical history, prior/concomitant medications, prior systemic therapies, and prior procedures will be summarized by treatment groups using the Randomized Set population.

8.1 Demographic and Baseline Characteristics

Continuous demographic data (e.g., age, height, and weight) will be summarized with N, mean, standard deviation (St. Dev.), median, minimum, and maximum. Frequencies and percentages will be computed for the following categorical parameters (but not limited to): sex, race, ethnicity, age group (< 55, 55 to < 65, 65 to < 75, 75 to < 85, and \geq 85 years old), tobacco and alcohol use (unknown, never, current, former), and ECOG performance status (0, 1, \geq 2).

Subject's baseline characteristics will be summarized, including (but not limited to) stratification factors, small cell lung cancer history (overall VALG stage at study entry/initial diagnosis, overall TNM at study entry/initial diagnosis, TNM staging (T, N, M) at study entry, weeks from initial diagnosis to randomization, DLL3 status, DLL3 expression in percentage), prior systemic therapies (sensitivity to first line platinum-based regimen, number of subjects who progressed prior to completion of platinum-based regimen, days from completion of prior regimen to progression for those who completed it, treatment received, reason for discontinuation of prior treatment), prior radiation therapy (number of subjects with any prior radiation, type of radiation, treatment intent, best outcome), prior procedures, electrocardiogram, and echocardiogram.

There will be no statistical comparison of demographic and baseline measurements between treatment arms.

8.2 Medical History

Medical history data will be summarized and presented using conditions/diagnoses as captured on the eCRF. The conditions/diagnoses will be presented in alphabetical order. The number and percentage of subjects with a particular condition/diagnosis will be summarized for each treatment arm. Subjects reporting more than one condition/diagnosis will be counted only once for that condition/diagnosis. There will be no statistical comparison of the medical history between treatment arms.

8.3 Prior and Concomitant Medications

A prior medication is defined as any medication with an end date prior to the date of randomization and collected on the electronic case report forms (eCRFs). A concomitant medication is defined as any drug that started on the day of or after randomization, but not more than 70 days after the last study drug administration. Medications with a start date prior to the date of randomization and continuing after randomization are also classified as concomitant medications. A medication will also be considered a concomitant medication if one of the following three cases occur: (1) the start date is missing and the end date is either after or on the day of randomization; (2) the start date is not missing but not more than 70 days after the last study drug administration and the end date is missing; (3) both the start date and the end date are missing.

Prior and concomitant medications will be summarized separately by the anatomical therapeutic chemical (ATC) codes in the World Health Organization (WHO) dictionary. Subjects reporting the same medication generic name two or more times will be counted only once for that generic name. Subjects reporting more than one medication will be counted only once in the total number of subjects taking a concomitant medication. In addition, the number of prior and concomitant medications will also be presented for each treatment arm.

There will be no statistical comparison of prior and concomitant medications between treatment arms.

